9.5.2.2 Efficacy variables

Efficacy data will be reported for patients overall. Results of all statistical analysis will be presented using a 95% confidence interval (CI), unless otherwise stated.

The following table (Table 13) details which endpoints are to be subjected to statistical analysis.

Table 13 Pre-planned statistical and sensitivity analyses to be conducted

Endpoints analyzed	Notes
Progression-free survival	Analysis by Kaplan Meier estimates using Investigator RECIST 1.1 assessments
Objective response rate	Analysis using Investigator RECIST 1.1 assessments
Duration of response	Analysis by Kaplan Meier estimates using Investigator RECIST 1.1 assessments, in patients with documented response
PFS at 6 and 12 months	Using the Kaplan Meier estimates of progression free survival at 6 and 12 months
Overall survival	Analysis by Kaplan Meier estimates
Overall survival at 6, 12 and 18 months	Using the Kaplan Meier estimates of OS at 6, 12 and 18 months
Time to deterioration (EORTC QLQ-C30 and QLQ-LC13 endpoints)	Analysis by Kaplan Meier estimates. Change from baseline values will be calculated.

EORTC European Organisation for Research and Treatment of Cancer; QLQ-C30 v3 30-item Core Quality of Life Questionnaire, version 3; QLQ-LC13 13-item Lung Cancer Quality of Life Questionnaire;

RECIST 1.1 Response Evaluation Criteria in Solid Tumors, version 1.1.

Progression-free survival

The PFS analysis will be based on the programmatically derived RECIST 1.1 using the Investigator tumor assessments. The analysis will be performed using Kaplan Meier plots. Summaries of the number and percentage of patients experiencing a PFS event will be provided along with median PFS and its 95% confidence interval. In addition, the proportion of patients who are progression-free at 6 and 12 months will be presented.

A subgroup analysis may be conducted comparing PFS in the following subgroups, assuming sufficient sample size per subgroup: platinum therapy receiving (carboplatin or cisplatin), age, gender, performance status, smoking status and CNS metastasis at baseline (Y/N).

Other baseline variables may also be assessed if there is clinical justification. The purpose of the subgroup analyses is to assess the consistency of treatment effect across expected prognostic and/or predictive factors.

For each subgroup, the HR and 95% CI will be calculated by Cox regression and a log-rank test will be provided.

Objective response rate

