The ORR will be based on the programmatically derived RECIST 1.1 using the investigator tumor data. Summaries will be produced that present the number and percentage of patients with a tumor response (CR/PR). 95% CI will also be presented.

Duration of response

DoR will be analyzed using the investigator tumor data in responding patients. Descriptive data will be provided for the DoR in responding patients, including the associated Kaplan-Meier curves.

Overall survival

OS will be analyzed using a Kaplan-Meier plots. Summaries of the number and percentage of patients who have died, those still in survival follow-up, those lost to follow-up, and those who have withdrawn consent will be provided along with the median OS and corresponding 95% CI. In addition, the proportion of patients alive at 6, 12, and 18 months will be presented.

A subgroup analysis may be conducted comparing OS in the following subgroups, assuming sufficient sample size per subgroup: platinum therapy receiving (carboplatin or cisplatin), age, gender, performance status, smoking status and CNS metastasis at baseline (Y/N).

For each subgroup, the HR and 95% CI will be calculated by Cox regression and a log-rank test will be provided.

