#### Endpoints analyzed:

- Progression-free survival (PFS): This analysis will be performed for the Intention-to-Treat population (ITT). PFS is defined as the time from the first date of treatment until the date of objective disease progression or death (by any cause in the absence of progression) regardless of whether the patient withdraws from IP or receives another anticancer therapy prior to progression.

**PFS (days)** = Date of event or Censor date – treatment start date +1

Patients who have not progressed or died at the time of analysis will be censored at the time of the latest date of assessment from their last evaluable assessment. However, if the patient progresses or dies after 2 or more missed visits, the patient will be censored at the time of the latest evaluable assessment prior to the 2 missed visits. If the patient has no evaluable visits or does not have baseline data, he/she will be censored at Day 1 unless he/she dies within 2 visits of baseline, in which case the date of death is the event date.

The PFS analysis will be based on the programmatically derived RECIST 1.1 using the Investigator tumor assessments. It will be analysed PFS, PFS at 6 months (6mPFS) and PFS at 12 months (12mPFS).

- Objective response rate (ORR): This outcome will be analysed for the responder's analysis set. The ORR will be based on the programmatically derived RECIST 1.1 using the investigator tumor data.
- Duration of response (DoR): This outcome will be analysed for the responder's analysis set. DoR is defined as the time from the date of first documented response per RECIST1.1 until the first date of documented progression per RECIST1.1 or death in the absence of disease progression.

DoR (days) = Date of PFS event or censoring – Date of first response +1

The end of response should coincide with the date of progression or death from any cause used for the PFS endpoint. If a patient does not progress following a response, then the patients' DoR will be censored at the PFS censoring time. DoR will not be defined for those patients who do not have a documented response. It will be analysed DoR and DoR at 1 year (DoR12)

- Overall survival (OS): This analysis will be performed for the Intention-to-Treat population (ITT). OS is defined as the time from the first date of treatment until death due to any cause.

OS (days) = Death date or Censor date - treatment start date +1

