## **5. ANALYSIS METHODS**

Descriptive statistics will be used for all variables, as appropriate. Continuous variables will be summarized by the number of observations, mean, standard deviation, median, quartiles (Q1 and Q3), minimum, and maximum. Categorical variables will be summarized by frequency counts and percentages for each category. The number of missing data will be provided for every analysed variable.

Missing values will not be considered for calculating percentages or any other descriptive, meaning that only valid values will be presented. No use of any method for the handling of missing data is foreseen.

For patients excluded from the statistical analyses, descriptive of the reasons for non-evaluability will be provided.

The software package SAS version 9.4 will be used for data analysis.

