#### Endpoints analyzed:

- Progression-free survival (PFS): The PFS analysis will be based on the programmatically derived RECIST 1.1 using the Investigator tumor assessments. The analysis will be performed using Kaplan Meier plots. Summaries of the number and percentage of patients experiencing a PFS event will be provided along with median PFS and its 95% confidence interval. In addition, the proportion of patients who are progression-free at 6 (PFS 6) and 12 (PFS 12) months will be presented.

A subgroup analysis may be conducted comparing PFS in the following subgroups, assuming sufficient sample size per subgroup: platinum therapy receiving (carboplatin or cisplatin), age ( $\geq 65$ ,  $< 65$ ), gender, performance status, smoking status, CNS metastasis at baseline (Yes/No) and number of chemotherapy cycles (5 or 6 cycles vs 4 or less cycles)

For each subgroup, the HR and 95% CI will be calculated by Cox regression and a log-rank test will be provided.

- Objective response rate (ORR): The ORR will be based on the programmatically derived RECIST 1.1 using the investigator tumor data. Summaries will be produced that present the number and percentage of patients with a tumor response (CR/PR). 95% CI will also be presented.

A subgroup analysis may be conducted comparing ORR in the following subgroups, assuming sufficient sample size per subgroup: platinum therapy receiving (carboplatin or cisplatin), age ( $\geq 65$ ,  $< 65$ ), gender, performance status, smoking status, CNS metastasis at baseline (Yes/No) and number of chemotherapy cycles (5 or 6 cycles vs 4 or less cycles). Results will be compared using Chi-Squared test.

- Duration of response (DoR): DoR will be analyzed using the investigator tumor data in responding patients. Descriptive data will be provided for the DoR in responding patients (continuous data), including the associated Kaplan-Meier curves. In addition, the DoR at 1 year (DoR 12) will be analyzed.

A subgroup analysis may be conducted comparing DoR in the following subgroups, assuming sufficient sample size per subgroup: platinum therapy receiving (carboplatin

or cisplatin), age ( $\geq 65$ ,  $< 65$ ), gender, performance status, smoking status, CNS metastasis at baseline (Yes/No) and number of chemotherapy cycles (5 or 6 cycles vs 4 or less cycles)

For each subgroup, the HR and 95% CI will be calculated by Cox regression and a log-rank test will be provided.

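### The SAP adds an ordinary continuous-data summary to duration of response, a censored endpoint, and names no Kaplan-Meier median, confidence interval or DoR12 estimator

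*SAP*

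**What the plan says.** SAP 4.2.2.1 defines DoR from first documented response to progression or death. For a responder who has not progressed, it says that "DoR will be censored at the PFS censoring time". DoR is therefore a censored time-to-event variable.

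SAP 5.2.1 then states the analysis: "Descriptive data will be provided for the DoR in responding patients (continuous data), including the associated Kaplan-Meier curves". For the one-year figure it says only: "In addition, the DoR at 1 year (DoR 12) will be analyzed". The optional DoR subgroup comparisons use survival methods: "For each subgroup, the HR and 95% CI will be calculated by Cox regression and a log-rank test will be provided".

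The tag in brackets has a defined meaning. SAP 5 says: "Continuous variables will be summarized by the number of observations, mean, standard deviation, median, quartiles (Q1 and Q3), minimum, and maximum". SAP 4.3 uses the same tag, variable by variable, as the instruction for what to tabulate.

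The protocol differs. Its table of pre-planned analyses in Section 9.5.2.2 (labelled Table 13 there) gives for DoR: "Analysis by Kaplan Meier estimates using Investigator RECIST 1.1 assessments, in patients with documented response". The text of that section reads: "Descriptive data will be provided for the DoR in responding patients, including the associated Kaplan-Meier curves". That is the SAP sentence without the tag.

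For PFS, SAP 5.2.1 asks for event counts "along with median PFS and its 95% confidence interval", and OS is handled likewise. DoR has no equivalent. The protocol table assigns Kaplan-Meier estimates to PFS at 6 and 12 months and to OS at 6, 12 and 18 months, but has no row for DoR at one year.

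**The concern.** A mean, SD, quartile or maximum computed on event and censoring times together treats every ongoing response as if it had ended at its last assessment. The patients affected are those whose responses have lasted longest, so the error runs one way: the reported duration is too short.

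A programmer could fairly take the tag as an instruction to run ordinary descriptive statistics. The only other effectiveness endpoint in SAP 5.2.1 that carries it is time to treatment discontinuation. That endpoint is restricted to patients who discontinued and has no Kaplan-Meier analysis, so there the tag does mean ordinary statistics.

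Two consequences follow. The study report could carry a DoR table that disagrees with its own Kaplan-Meier curve. And DoR12, a named secondary endpoint, could be computed in more than one way, because no estimator is fixed.

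**Working it through.** The documents state no expected DoR, DoR12 or censoring fraction, so there is no plan figure to reproduce. The size has to be worked out under stated assumptions.

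**Inputs from the documents.** Accrual is about 6 months (SAP 2.2). Last enrolment is Q2 2021 and last completion Q2 2022 (Protocol 1.2), so the planned cutoff F is about 12 months after last entry. The first scan is recommended at week 9, about 2.1 months, and scans are at most 12 weeks (2.76 months) apart (Protocol Table 1).

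**Assumptions.** DoR (T) is exponential with true median m = 4, 5 or 6 months. Entry is uniform over 6 months. First response falls at 2.1 months. The last scan falls uniformly 0 to 2.76 months before cutoff. The censoring time is then C = F − 2.1 + U(0, 6) − U(0, 2.76).

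**Mean.** For exponential T with rate λ = ln 2/m, E[min(T, C)] = (1/λ) × P(T ≤ C). The naive mean is therefore too low by exactly the censored fraction c:

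c = exp(−λ(F − 2.1)) × (1 − exp(−6λ))/(6λ) × (exp(2.76λ) − 1)/(2.76λ)

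With m = 5 and F = 12, λ = 0.1386 and c = 0.2535 × 0.6789 × 1.2182 = 0.210. The true mean is 5/ln 2 = 7.2 months and the naive mean is 7.2 × 0.790 = 5.7 months. In full:

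| Cutoff after last entry | m = 4 (true mean 5.8) | m = 5 (true mean 7.2) | m = 6 (true mean 8.7) |
|---|---|---|---|
| 12 months | 4.9 (14.3% low) | 5.7 (21.0% low) | 6.3 (27.1% low) |
| 15 months | 5.3 (8.5% low) | 6.2 (13.8% low) | 7.0 (19.1% low) |
| 18 months | 5.5 (5.1% low) | 6.6 (9.1% low) | 7.5 (13.5% low) |

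**Median.** At F = 12 the shortest possible censoring time is 12 − 2.1 − 2.76 = 7.1 months. A true median of 4 to 6 months lies below that, so the naive median is unaffected apart from sampling error. With cutoff only 9 months after last entry the shortest is 4.1 months, and simulation shows the naive median falling by up to 8% at m = 6.

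**Upper quartile.** The naive value q solves P(T > q) × P(C > q) = 0.25. At m = 5 and F = 12, q = 9.1 gives 0.283 × 0.883 = 0.25, against a true upper quartile of 2 × 5 = 10 months.

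**DoR12 as a crude proportion.** If it were the share of responders with observed duration of at least 12 months, its expectation would be P(T ≥ 12) × P(C ≥ 12).
- F = 12: P(C ≥ 12) = (6 − 2.1 − 1.38)/6 = 0.42. At m = 5 the true value is 2^(−12/5) = 19%, and the crude value is 0.42 × 19% = 8%.
- F = 15: P(C ≥ 12) = 1 − (1.86²/5.52)/6 = 0.90, giving 17% against 19%.
- F = 18: the shortest censoring time is 13.1 months, so there is no bias.

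**Cross-check that Kaplan-Meier removes the bias.** A separate simulation used 57 responders, response at 2 months, no scan lag and F = 12. At m = 5 the naive mean was 6.0 against a true 7.2 months. The naive and Kaplan-Meier medians were both 5.1. Crude DoR12 was 12.6%, and Kaplan-Meier DoR12 was 19.0% against a true 18.9%.

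**The case against.** A reader might infer that the SAP ignores censoring for DoR. It does not. The sentence with the tag also plans Kaplan-Meier curves, SAP 4.2.2.1 has an explicit censoring rule, and the subgroup comparisons use Cox regression and the log-rank test. A valid median and 12-month value can be read from the planned curve. This part of the objection stands: the defect is an unsuitable added summary with missing specification, not a plan without survival methods.

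A reader might also infer that DoR12 will come out too low. The SAP does not say so. No crude proportion is prescribed, and none of the continuous statistics in SAP 5 is a 12-month share. The figure of 8% against 19% describes one calculation that the wording leaves open.

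The size also depends on the cutoff. The dates in the protocol are estimates, and recruitment may be shortened or extended. Survival at 18 months is a planned endpoint, so longer follow-up is plausible, and the bias shrinks with it. Scan lag matters too: without it, crude DoR12 at a 5-month median is about 12% to 13% rather than 8%.

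Finally, DoR is one of several secondary endpoints in a descriptive single-arm study whose primary endpoints concern safety, and no decision rests on its mean. This lowers the severity. It does not make the mean, SD or upper quartile of partly censored times valid estimates of response duration.

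**Conclusion.** The point holds in limited form. SAP 5.2.1 attaches a summary to DoR that cannot use the censoring defined in SAP 4.2.2.1. This departs from the protocol's Kaplan-Meier plan and leaves the DoR median, its confidence interval and the DoR12 estimator unnamed.

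Under the stated assumptions the naive mean is clearly short at each cutoff examined, and less so as follow-up lengthens. The upper quartile is also short at the 12-month cutoff. The median is essentially unaffected at 12 months or later. These sizes rest on an exponential shape and a 4- to 6-month median that the documents do not give; longer responses or an earlier cutoff would widen the gap.

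For DoR12 the finding is an unspecified estimator, not a demonstrated bias. Severity: should-fix.

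**What to change.** In SAP 5.2.1, for DoR:
- delete the continuous-data tag;
- report the number of responders with an event and the number censored;
- report the Kaplan-Meier median and quartiles with 95% CI;
- define DoR12 as the Kaplan-Meier estimate at 12 months from first response, with 95% CI.

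This brings the SAP into line with the protocol table and with its own treatment of PFS and OS. The cost is a wording change and one standard survival table. It needs no new data and is best done before the tables are programmed.

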#### Endpoints analyzed:

- Change from baseline in European Organisation for Research and Treatment of Cancer Quality of Life Questionnaire Core 30 items (EORTC QLQ-C30) and Questionnaire-Lung Cancer 13 (EORTC QLQLC13):

Scores for the QLQ-C30 and QLQ-LC13 questionnaires will be calculated according to published scoring manuals or the developer's guidelines. Raw scores from scales in both questionnaires will be standardized by linear transformation so that they range from 0 to 100. Higher scores for symptom items indicate greater symptom severity, while higher scores for function and global health status/QoL items indicate better function and health status/QoL. For both questionnaires, a clinically meaningful change will be prespecified as an absolute change in score from baseline of  $\geq 10$  points (either deterioration or improvement). For the five key disease-related symptoms (cough, dyspnea, and chest pain [QLQ-LC13], and fatigue and appetite loss [QLQ-C30]), changes at each visit from baseline to disease progression or end of follow-up (whichever came first) will be analyzed using a mixed model for repeated measures (MMRM) to derive an overall adjusted mean change from baseline, reflecting the average treatment effect over visits. The model assumes PROs will be collected at multiple visits per

patient. Visits with >75% missing data will be excluded from the analysis. The MMRM included treatment, age at baseline (<65 vs ≥65 years), sex, smoking history (smoker vs non-smoker) and visit interaction as fixed factors, and baseline score as a covariate; the model further adjusted for baseline score-by-visit interaction.

Summaries of original and change from baseline values of each symptom scale/item, the global HRQoL score, and each functional domain will be reported by visit.

Time to symptom deterioration and time to quality of life / function deterioration (defined in 4.2.2) will be analyzed by product limit methods to provide summaries of the number and percentage of patients experiencing a clinically meaningful deterioration or death, the median time to deterioration together with the corresponding 95% CIs, as well as the Kaplan-Meier plot. An stratified log-rank test adjusted for therapy will be used with HR s and 95% CIs calculated using a stratified Cox proportional hazards model.

Symptom improvement rate and Quality of life / function improvement (defined in 4.2.2) will be summarized.

- Changes from baseline in PRO-CTCAE:

PRO-CTCAE data will be presented using summaries and descriptive statistics for categorical data for each question of the questionnaire.

### 5.2.3 Secondary outcome 3

- To describe health care resources use related to management of ES-SCLC patients treated with durvalumab in combination with platinum- etoposide as first-line treatment. It will be described the overall costs and health care resources use as well as costs and health care resources use adjusted by time in years.

The following data will be described as appropriate:

- Number of hospitalizations (Categorical and continuous)
- Length of hospitalizations: time from date of admission to discharge date (Continuous).
- Number of visits to oncology service (Categorical and continuous)
- Number of emergency visits (Categorical and continuous)
- Number of outpatients visits (Categorical and continuous)
- Number of imaging tests (Categorical and continuous)
- Number of biopsy-related procedures (Categorical and continuous)
- Listing of treatments administered, including: Treatment name, dose, duration and number of cycles
- Assessment of health economic resource: Costs associated with HCRU use will be quantified by multiplying the natural units of use of each resource by the cost of each resource retrieved from Spanish databases

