9.5.2.3 Patient reported outcomes

Summary measures of visit and overall compliance and completion rates will be derived for each PRO questionnaire. Refer to the SAP for details.

For PRO symptoms and health related quality of life endpoints, the main concepts of interest have been identified using a literature review, and detailed qualitative interviews SCLC patient and clinicians. The key symptoms were: cough, hemoptysis, dyspnea, chest pain, insomnia, fatigue and appetite loss.

Therefore we would like to pre-specify that an effective treatment would reduce time to deterioration and effect mean change from baseline in these key SCLC symptoms. The prespecified symptomatic endpoints are as follows: time to deterioration from baseline of cough, hemoptysis, dyspnea and chest pain from EORTC QLQ- LC13; and insomnia, fatigue and appetite loss from EORTC QLQ -C30; as well as average mean change of the key symptoms.

In addition, physical functioning and overall health status domains of the EORTC QLQ-C30 are furthermore pre-specified endpoints of interest.

The detail how this data will be analysed and the effect we would like to see to determine a symptomatic treatment effect will further be detailed and pre-specified in the SAP.

(a) EORTC QLQ-C30

If possible, time to symptom deterioration will be summarized for each of the 3 symptom scales (fatigue, pain, nausea/vomiting) and the 5 individual symptom items (dyspnea, insomnia, appetite loss, constipation, diarrhea). Similarly, a summary of QoL/function deterioration will be summarized for each of the function scales (physical, role, emotional, cognitive, and social) and global health status/QoL. This will be achieved by using Kaplan-Meier product limit methods to provide summaries of the number and percentage of patients experiencing a clinically meaningful deterioration or death, the median time to deterioration together with the corresponding 95% CIs, as well as the Kaplan-Meier plots.

Summaries of original and change from baseline values of each symptom scale/item, the global HRQoL score, and each functional domain will be reported by visit. Details will provided in the SAP.

Definition of clinically meaningful changes

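### The protocol pre-specifies average mean change for seven key symptoms; the SAP derives it for five and omits hemoptysis and insomnia without giving a reason

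*SAP*

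**What the plan says.** Protocol 9.5.2.3 states that the main concepts came from a literature review and from interviews with patients and clinicians, and then fixes the list: "The key symptoms were: cough, hemoptysis, dyspnea, chest pain, insomnia, fatigue and appetite loss". It pre-specifies time to deterioration for each of the seven, "as well as average mean change of the key symptoms". A separate sentence adds that "physical functioning and overall health status domains of the EORTC QLQ-C30 are furthermore pre-specified endpoints of interest". How the data are to be analysed, and what effect would count, "will further be detailed and pre-specified in the SAP".

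SAP 5.2.2 opens its model-based analysis with "For the five key disease-related symptoms" and names cough, dyspnea and chest pain from the QLQ-LC13 and fatigue and appetite loss from the QLQ-C30. Change from baseline for these five "will be analyzed using a mixed model for repeated measures (MMRM) to derive an overall adjusted mean change from baseline". The next paragraph promises "Summaries of original and change from baseline values of each symptom scale/item, the global HRQoL score, and each functional domain", reported by visit. Time to deterioration and improvement rates follow. Hemoptysis and insomnia are not in the model, and no reason is given anywhere in the SAP.

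**The concern.** The protocol fixes a list of key symptoms and attaches an average-change measure to it. The SAP describes five of the seven as if they were the whole list. A reader of the final report would see an average change for five symptoms and could not tell that two more had been pre-specified on the same footing.

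The stakes are modest. The study has no formal hypothesis and patient-reported outcomes are a secondary objective. But an unexplained difference between protocol and SAP in which symptoms get the headline estimate invites questions later, and it costs very little to avoid.

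**Working it through.** No power or error-rate formula applies. The check compares two lists.

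**Protocol 9.5.2.3, key symptoms**
- QLQ-LC13: cough, hemoptysis, dyspnea, chest pain (4)
- QLQ-C30: insomnia, fatigue, appetite loss (3)
- Total: 4 + 3 = 7

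**SAP 5.2.2, symptoms in the mixed model**
- QLQ-LC13: cough, dyspnea, chest pain (3)
- QLQ-C30: fatigue, appetite loss (2)
- Total: 3 + 2 = 5, which agrees with the SAP's own count

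**Difference**
- 7 − 5 = 2: hemoptysis (QLQ-LC13) and insomnia (QLQ-C30)
- 2 / 7 = 0.286, or 29%
- The SAP adds no symptom that is absent from the protocol's list.

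**What the two omitted symptoms keep.** The by-visit paragraph of SAP 5.2.2 stands under a heading that covers both questionnaires, so raw values and change from baseline are tabulated for both symptoms. SAP 4.2.2.2 also keeps time to symptom deterioration and symptom improvement rate for both instruments.

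**Whether that replaces the average change.** It does not.
- A table of means by visit gives no single average across visits. In the SAP only the model does.
- The by-visit tables use observed values only, without imputation (SAP 5 and 6.2), whereas the mixed model uses a patient's repeated measurements jointly. In a disease where the earlier phase III trial reported a median survival of 13.0 months on this combination (Protocol 2.3.1.2), later visits will describe a shrinking group. Symptoms of equal standing in the protocol are thus treated differently with respect to drop-out.
- The other fallback has a fault of its own. SAP 4.2.2.2 defines symptom deterioration as a fall of at least 10 points and symptom improvement as a rise, while SAP 5.2.2 says that higher symptom scores are worse. The protocol's text definition of time to symptom deterioration uses a rise. This is a separate matter, but it weakens these analyses as substitutes.

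**The model itself.** SAP 5.2.2 lists treatment among the fixed factors and speaks of an average treatment effect. SAP 6.1.1 confirms a single-arm study. A treatment factor then has one level and cannot be separated from the intercept, so the model has to be corrected before it is extended.

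**The case against.** The strongest reply is that the protocol leaves the analysis of these data to the SAP, never names a mixed model, and calls all analyses descriptive. Choosing which scales receive an extra model could be seen as within that remit, and every scale is still reported. Part of this stands: the method is for the SAP to choose, and nothing disappears from the report. But what is delegated is how the data are analysed and what effect is sought. The list of key symptoms is already settled in the protocol, together with an average-change measure, and delegation does not cover shortening it without comment.

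A second reply is that the protocol does not define average mean change, so by-visit means might satisfy it. That is possible. The SAP's own reading, however, is a single average over visits, and it supplies that for five symptoms only.

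A reader might also infer more than the documents support:
- **That four of nine endpoints lose a promised average change.** Seven symptoms plus two domains make nine, and 9 − 5 = 4 do lie outside the model. But the protocol attaches the average-change measure to the key symptoms only. Physical functioning and overall health status are called endpoints of interest with no such measure named, and their by-visit change and time to deterioration remain.
- **That this is selective analysis.** Nothing points to outcome-driven choice. The five symptoms are those that Protocol 2.3.1.2 reports as pre-specified in the earlier phase III trial, which suggests a carried-over list. That is an inference, but the treatment term in a single-arm model fits it.
- **That the SAP's empty amendment history shows an undocumented change.** That table records changes between SAP versions, not differences from the protocol.

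**Conclusion.** The mismatch is real and small. Two of seven pre-specified key symptoms, hemoptysis and insomnia (29%), do not receive the average change that Protocol 9.5.2.3 sets out, and SAP 5.2.2 gives no reason. They lose one summary measure, not their place in the analysis. The conclusion assumes that average mean change means an average over visits, as the SAP itself implements it. On a looser reading, what remains is a five-symptom list presented as the key list without justification. Either way this is a worthwhile tidy-up of a descriptive secondary objective; it does not threaten the study's conclusions.

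**What to change.** In SAP 5.2.2:
1. Replace the five-symptom list with the protocol's seven by adding hemoptysis (QLQ-LC13) and insomnia (QLQ-C30) to the mixed model.
2. Remove the treatment term and the reference to an average treatment effect. The target is then the adjusted mean change from baseline over visits in one cohort.
3. Optionally, add physical functioning and global health status/QoL to the same model, labelled as an extension beyond what the protocol asks for.

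If the sponsor prefers to keep five symptoms, the SAP should say that the protocol lists seven and give the reason for the shorter list.

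The list should be settled before quality-of-life results are seen; SAP 7 schedules an analysis of section 5.2.2 for February 2022. No new data are needed. The cost is two more model runs, or four with the two domains, plus a short text change.
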